### 1.3.1 EZH2 in sarcomas

INI1 is a potent tumor suppressor gene, a member of the SWI/SNF complex whose integrated functions control diverse cellular processes such as differentiation and proliferation. Loss of INI1 function leads to elevated expression and recruitment of EZH2 to target genes that become trimethylated on H3K27 and repressed, which results in the upregulation of several oncogenic signaling pathways, including Sonic Hedgehog, Wnt/β-Catenin, and MYC. INI1 loss was first identified in malignant rhabdoid tumors (MRTs) which are rare and aggressive cancers that principally occur in childhood and can arise in various locations, mainly the kidney, brain, and soft tissues. MRTs harbor recurrent and specific biallelic-inactivating mutations or deletions of INI1 located in the 22q11.2 region. Interestingly, apart from this specific alteration, MRTs have a remarkably low rate of mutations and no genomic instability, suggesting a potential oncogenic driver role of INI1 loss in MRT tumorigenesis. INI1 loss has also been found

with high frequency (50 to 80%) in epithelioid sarcomas or other sarcomas with epithelioid features such as malignant peripheral sheath tumors (MPNSTs).

EZH2 overexpression has been noted in MPNST, compared to normal nerves, and neurofibroma, and levels appear to be 8-fold higher compared to atypical plexiform neurofibromas. It has shown that EZH2 directly inhibits miR-200b expression in MPNST, which may ultimately also contribute to epithelial-mesenchymal transition (EMT) progression, MPNST invasion and metastasis. EZH2 has been shown to be a critical regulator of epithelial-mesenchymal transition (EMT), which is a critical step for initiation of cancer invasion and metastasis. EZH2 promotes EMT directly by inhibiting the expression of E-cadherin and indirectly through the NF-κB/Twist pathway. Additionally, miR-200b is known to act as an inhibitor of EMT by targeting the transcription factor ZEB1/2 and then by activating E-cadherin. MPNSTs typically have known mutations in SUZ12 (56%) and EED (32%).

EZH2 knockdown by RNA interference in MPNST cell lines induced MPNST cell apoptosis in vitro and inhibits MPNST tumor growth in vivo, suggesting that EZH2 is a potential therapeutic target in MPNST. Zhang et al found that pharmacological inhibition of EZH2 by DZNep depleted EZH2 expression, induced expression of miR-30a and miR-30d, and inhibited Karyopherin β1 (KPNB1) expression in MPNST cells. By impairing the EZH2/miR-30a,d/KPNB1 pathway, DZNep induced MPNST cell apoptosis and cell cycle arrest, which together decreased MPNST cell viability and suppressed cell survival in vitro. They also demonstrated that DZNep treatment inhibited MPNST tumor initiation and growth rates in a mouse xenograft model.

#### 1.4 Overview of Clinical Studies

Tazemetostat (EPZ-6438) is a potent and highly selective, first-in-class oral small molecule EZH2 inhibitor. Tazemetostat has been shown to have anti-tumour activity in *in vitro* and xenograph models of EZH2- mutant B-cell non-Hodgkin lymphoma, INI1-negative malignant rhabdoid tumor, and SMARCA4-negative malignant rhabdoid tumor of the ovary.

##### 1.4.1 Hematologic malignancies

A Phase 1 study for relapsed/refractory solid tumors and B cell lymphoma (NCT01897571) was conducted with the primary endpoint being the maximum tolerated dose of Tazemetostat. Tazemetostat was administered

orally from 100 mg twice daily to 1600 mg twice daily in 28-day cycles between June 13, 2013, and Sept 21, 2016. 64 patients (21 with B-cell non-Hodgkin lymphoma, and 43 with advanced solid tumors) received Tazemetostat, the most common treatment-related adverse events were asthenia (21 [33%] of 64 treatment-related events), anemia (nine [14%]), anorexia (four [6%]), muscle spasms (nine [14%]), nausea (13 [20%]), and vomiting (six [9%]), usually grade 1 or 2 in severity. The recommended phase 2 dose was determined to be 800 mg twice daily. Durable objective responses, including complete responses, were observed in eight (38%) of 21 patients with B-cell non-Hodgkin lymphoma and two (5%) of 43 patients with solid tumors. Tazemetostat showed a favorable safety profile and antitumor activity in patients with refractory B-cell non-Hodgkin lymphoma and advanced solid tumors, including epithelioid sarcoma.

An interim update from a Phase 2 multicenter study using Tazemetostat in patients with relapsed or refractory follicular lymphoma showed that Tazemetostat was generally well tolerated, with 5% patients discontinued treatment due to a treatment-related AE, 9% patients needing a dose reduction due to a treatment-related AE, low rate of grade  $\geq 3$  treatment related AEs and no treatment related deaths. This study demonstrated durable, single agent, antitumor activity in difficult-to-treat patients with relapsed / refractory follicular lymphoma with an ORR of 77% and 34% in MT (mutant type) and WT (wild type) EZH2, respectively. All patients in the MT cohort and a majority of patients in WT cohort demonstrating a reduction in tumor volume. There was durable clinical activity across both MT and WT cohorts, with patients on therapy up to 23 months, and responses continuing to deepen over time, with a PFS of 11.1 and 5.7 months in MT and WT EZH2, respectively.

An open-label, single-arm, phase 2 trial done at 38 clinics or hospitals in France, the UK, Australia, Canada, Poland, Italy, Ukraine, Germany, and the USA using Tazemetostat 800 mg twice daily in patients with relapsed/refractory follicular lymphoma (NCT01897571). This study showed meaningful clinical activity and durability of response in patients with recurrent/refractory follicular lymphoma, with ORR pronounced in patients with EZH2 activating mutations. Late onset responses have been reported on Tazemetostat. Tazemetostat was generally well tolerated in heavily pretreated patients with relapsed or refractory follicular lymphoma. Between July 9, 2015, and May 24, 2019, 99 patients (45 in the EZH2mut cohort and 54 in the EZH2WT cohort) were enrolled in the study with median follow-up of

22 months for the EZH2MT cohort and 35.9 months for the EZH2WT cohort. The objective response rate was 69% (95% CI 53–82; 31 of 45 patients) in the EZH2mut cohort and 35% (23–49; 19 of 54 patients) in the EZH2WT cohort. Median duration of response was 10.9 months (95% CI 7.22–not estimable [NE]) in the EZH2mut cohort and 13 months (5.6–NE) in the EZH2WT cohort; median progression-free survival was 13.8 months (10.7–22.0) and 11.1 months (3.7–14.6). Among all 99 patients, treatment-related grade 3 or worse adverse events included thrombocytopenia (3%), neutropenia (3%), and anemia (2%). Serious treatment-related adverse events were reported in four (4%) of 99 patients. There were no treatment-related deaths.

In 2016, the Food and Drug Administration (FDA) granted Tazemetostat Fast Track status in 2016 for patients with relapsed/refractory DLBCL with EZH2-activating mutations. On June 18, 2020, the Food and Drug Administration (FDA) granted accelerated approval to Tazemetostat for adult patients with relapsed or refractory (R/R) follicular lymphoma whose tumors are positive for an EZH2 mutation and who have received at least 2 prior systemic therapies, and for adult patients with R/R follicular lymphoma who have no satisfactory alternative treatment options.

Tazemetostat is still being evaluated as a combination therapy in ongoing clinical trials. One study is evaluating Tazemetostat in combination with R-CHOP (NCT02889523), a chemotherapy regimen, as a first-line treatment for newly diagnosed elderly, high-risk patients with diffuse large B-cell lymphoma (DLBCL), the most common type of NHL. Another clinical trial (phase 1) is evaluating Tazemetostat in combination with Tecentriq™ (atezolizumab), in patients with relapsed or refractory DLBCL. Tecentriq is an anti-PD-L1 cancer immunotherapy approved by FDA, and in a phase 1b study as a combination therapy with prednisolone, in patients with relapsed or refractory DLBCL (NCT02220842, NCT01897571).

#### 1.4.2 Solid tumors

There are preclinical data on impact of inhibition of EZH2 overexpression in various solid tumors, including MPNST, but degree of downstream effects is tumor dependent and overall clinical impact in terms of response rates in MPNST is unknown. Tazemetostat has been shown to have antitumor activity in preclinical malignant rhabdoid tumor (MRT) models that were negative for the INI1 protein and in phase I trials of MRT and epithelioid sarcoma. In an open-label, phase 2 basket study, patients were enrolled from 32 hospitals and clinics in Australia, Belgium, Canada, France, Germany,

Italy, Taiwan, the USA, and the UK into seven cohorts of patients with different INI1-negative solid tumors or synovial sarcoma (NCT02601950). Patients eligible for the epithelioid sarcoma cohort (cohort 5) were aged 16 years or older with histologically confirmed, locally advanced or metastatic epithelioid sarcoma; documented loss of INI1 expression by immunohistochemical analysis or biallelic SMARCB1 (the gene that encodes INI1) alterations, or both. Patients received Tazemetostat 800 mg orally twice per day in continuous 28-day cycles and primary endpoint was objective response rate per RECIST 1.1. Between Dec 22, 2015, and July 7, 2017, 62 patients with epithelioid sarcoma were enrolled in the study. Tazemetostat was well tolerated and showed clinical activity in this cohort of patients with advanced epithelioid sarcoma. Nine (15%) of 62 patients had an objective response at data cutoff (Sept 17, 2018). At a median follow-up of 13.8 months, median duration of response was not reached (95% CI 9.2 -not estimable). 16 (26%) patients had disease control at 32 weeks. Median time to response was 3.9 months. Median progression-free survival was 5.5 months (95% CI 3.4-5.9), and median overall survival was 19 months (11-not estimable). Grade 3 or worse treatment-related adverse events included anemia (6%) and weight loss (3%), without treatment-related deaths. A phase 1b/3 trial of Tazemetostat plus doxorubicin in the front-line setting is currently underway (NCT04204941).

Breast cancer gene 1 (BRCA1)-associated protein 1 (BAP1), a nuclear deubiquitinase, is commonly inactivated in malignant mesothelioma and preclinical data showed that BAP1 inactivation sensitizes mesothelial cells to inhibition of EZH2. A 2-part, open label phase 2 study evaluated the safety and efficacy of Tazemetostat in relapsed/refractory (R/R) malignant mesothelioma with BAP1-inactivation (NCT02860286). Primary endpoints were PK profiling of Tazemetostat in all patients (part 1), and disease control rate (DCR) at week 12 in patients with BAP1-deficient R/R malignant mesothelioma (part 2). Secondary endpoints included safety, overall response rate (ORR), progression-free survival, overall survival, and duration of response (DOR). The study enrolled 74 patients with R/R malignant mesothelioma, of which 70 (95%) were centrally confirmed to be BAP1-deficient. Median prior lines of therapy were two. The 12-week DCR was 47% (n = 35). The ORR per RECIST version 1.1 was 3% [complete response: 0%; partial response (PR): 3% (n = 2)]. Of the 2 patients with PR, 1 had a duration of response (DOR) of 21 weeks and the other is ongoing (15.3 weeks at data cut off). 47 subjects (64%) and 21 subjects (28%) had stable disease (SD) and progressive disease, respectively. Overall, 91% of subjects discontinued,

either due to disease progression (n = 65), death (n = 5), or treatment discontinuation (n = 1). Grade  $\geq 3$  treatment-emergent adverse events occurred in  $\leq 5\%$  of patients, most commonly anemia (5%) and dyspnea (4%). No subjects discontinued due to treatment-emergent adverse events and there were no treatment-related deaths. Based on disease control rate and stable disease, Tazemetostat showed antitumor activity in patients with BAP1-deficient R/R malignant mesothelioma.

Recent literature has described genomic features of small cell carcinoma of the ovary of the hypercalcemic type (SCCOHT), a rare highly aggressive tumor that affects young women. This cancer was found to have loss-of-function mutations in SMARCA4 (Brahma-related gene 1, BRG1) as a highly recurrent event in SCCOHT. SMARCA4 encodes one of the two possible catalytic subunits of the Switch/Sucrose Non-Fermentable chromatin-remodeling complex. Others have since confirmed this finding, with SMARCA4 mutations being found in over 90% of cases.

#### 1.4.3 Pediatrics

Tazemetostat is among the first investigational therapies to be tested in the multicenter, phase II Pediatric MATCH trial, which is being sponsored by the National Cancer Institute. The trial is examining targeted agents in children with advanced metastatic/recurrent tumors that are refractory and have EZH2, SMARCA4, or SMARCB1 gene mutations. The primary endpoint is ORR, with a secondary endpoint of PFS and additional evaluations of biomarker predictors of treatment response and change in tumor dynamics (NCT03213665, NCT03155620).

#### 1.5 Rationale for Regimen/Doses/Schedule

EPZ-6438 (Tazemetostat) is a selective small molecule inhibitor of the histone methyltransferase EZH2. Tazemetostat is an inhibitor of both wild type and mutated EZH2 containing residues Y646, A682G and A692 with half maximal inhibitory concentrations (IC50) ranging from 2-38 nmol/L. The compound shows a 35-fold selectivity over the most closely related HMT, EZH1, and greater than a 4500-fold selectivity over other HMTs. It selectively inhibits H3K27 methylation in a concentration and time dependent manner leading to selective killing of cell lines, specifically, human lymphoma cell lines with mutant or wildtype EZH2, *SMARCB1*-deficient malignant rhabdoid tumor (MRT) cell lines, and SMARCA2/A4 negative SCCOHT cell lines with IC50 in the nanomolar range. Tazemetostat administered orally has demonstrated antitumor activity *in vivo* against several EZH2 wild type and mutant human lymphoma xenograft murine models.

*SMARCB1* mutant MRT xenografts treated for 21-28 days demonstrated near elimination of the tumors with no regrowth observed. The MRT tumors demonstrated strong inhibition of H3K27Me3 which correlated with anti-tumor activity.

#### 1.5.1 Rationale for Doses Indicated in Current Study

The first pediatric phase 1 study of Tazemetostat (EZH-102, NCT02601937) for children with relapsed/refractory MRT including CNS ATRT and other INI-deficient tumors and synovial sarcoma enrolled its first patient in January 2016 and completed the dose escalation phase of the trial (dose expansion is ongoing). As of July 2017, the RP2D was determined to be 1200 mg/m^2 twice daily (for CNS primary tumors). The dose that will be utilized in the current protocol for children is lower (520mg/m^2 twice daily, up to a maximum of 800 mg per dose), due to the non-CNS MPSNT subjects under study.

For adults, the current study proposes 800mg twice daily, which is the dose studied in the previous described hematologic and solid tumor trials. 39, 41, 43

Additional information, including animal toxicology data, is provided in the Investigator's Brochure (IB) for Tazemetostat.

## 2. OBJECTIVES AND ENDPOINTS

### 2.1 Primary

#### 2.1.1 Primary Objective:

To assess the objective response rate of Tazemetostat in subjects with recurrent/refractory and/or metastatic MPNST

#### 2.1.2 Primary Endpoint:

Objective response rate (ORR, defined as proportion of subjects who achieve complete response CR or partial response PR) based on radiographic evaluation of treatment response via RECIST1.1.

### 2.2 Secondary

#### 2.2.1 Secondary Objectives:

- To determine the progression free survival (PFS) in subjects with recurrent/refractory and/or metastatic MPNST.
- To determine the time to progression (TTP) in subjects with recurrent/refractory and/or metastatic MPNST.

- To determine the clinical benefit using subject reported outcome (PRO)
- To assess the clinical benefit rate (CBR).

#### 2.2.2 Secondary Endpoints:

- PFS, defined as the duration of time from start of treatment to time of progression (RECIST 1.1 criteria) or death, whichever occurs first.
- TTP, defined as the length of time from the start of treatment until the evidence of disease progression, as defined by RECIST 1.1 criteria.
- Patient Reported Outcome (PRO) Numbered Pain Rating Scale 11 pain score mean (Appendix I).
- Clinical Benefit Rate (CBR), defined as the proportion of subjects with objective response (CR or PR) or stable disease (SD) lasting  $\geq 4$  months.

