### 3. STUDY DESIGN

#### 3.1 Study Overview

This is a single institution, open label, single-arm phase 2 trial. We plan to accrue up to 50 subjects in order to meet our goal of 29 evaluable subjects. Each subject will be administered Tazemetostat orally twice daily for subjects with recurrent and/or metastatic MPNST. Subjects will be dosed in continuous 28 day cycles, and as follows:

- Pediatric (12y- <18y): 520 mg/m^2/dose orally BID, not to exceed 800 mg orally twice daily
- Adult: ( $\geq 18$ y): 800 mg orally BID (flat dose for adults)

Surveillance imaging of primary and metastatic sites will be performed every 2 cycles, +/- 7 days after Cycle 1 Day 1, until disease progression or death. ctDNA testing results will be collected whenever performed per standard of care.

Response to treatment will be evaluated via RECIST 1.1. Treatment with Tazemetostat will continue until disease progression, unacceptable toxicity or withdrawal of consent or termination of study. Screening data will be reviewed to determine subject eligibility. Subjects who meet all inclusion criteria and none of the exclusion criteria will be entered into the study.

Total duration of subject participation will be 24 months. Total duration of the study is expected to be 36 months.

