## 6.1 Schedule of Events

Procedure:	Visit:	SCREENING (Windows outlined in Section 6.2)	CYCLE 1	CYCLES 2 AND BEYOND (WITHIN 72 HRS PRIOR)	END OF TREATMENT (WITHIN 14 DAYS OF LAST STUDY DRUG ADMINISTRATION)	FOLLOW UP (28 +/- 7 DAYS AFTER LAST DOSE OF TREATMENT)	SURVIVAL FOLLOW UP EVERY 90 +/- 14 DAYS AFTER LAST DOSE
Informed Consent		X					
Medical History, Demographic Information		X					
Clinical Exam		X	X	X	X		
Performance status (PS) 		X	X	X	X		
Vital Signs (VS) including height  , weight, and BSA 		X	X	X	X		
Numbered Pain Rating Scale 			X	X	X		
Labs (CBC diff, CMP) 		X	WEEKLY 	X			X 
Pregnancy Test (Urine or Serum) 		X	X	X			
INR		X					
Tibial x-ray 		X		X 			
Provide Study Drug for home administration			X	X			
Tumor disease evaluation 		X		EVERY 2 CYCLES 	X		
Tumor NGS 		X					
Circulating tumor DNA (ctDNA) 				X	X		
Provide and/or Review Subject Diary			X	X	X		
Concomitant Medication Review 		X	X	X	X		
Adverse Event Review 			X	X	X	X	
Survival Assessment							X

Abbreviations: VS=vital signs (blood pressure, temperature, pulse and respiratory rates, weight and height); CBC/diff=complete blood count and white blood cell differential; CMP = complete metabolic profile (sodium, potassium, chloride, bicarbonate, blood urea nitrogen, creatinine, glucose, alkaline phosphatase, AST, ALT, total bilirubin, protein), NGS Next Generation Sequencing

1 Performance status: Pediatric Karnofsky for subjects  $\geq$  16 years of age and Lansky for subjects 12-15 years of age; Adult ECOG score (18+)

UF-SC-001

2024-Aug-12

- 2 Numbered Pain Rating Scale , refer to Appendix G.
- 3 Laboratory tests at baseline need not be repeated if therapy starts within 72 hours of obtaining labs to assess eligibility. Labs are to be collected weekly for Cycle 1 (Days 1, 8, 15, and 22) +/- 72 hours. If patients have Grade 4 neutropenia then CBCs should be checked at least every other day until recovery to Grade 3 or until meeting the criteria for dose limiting toxicity. Automated differentials acceptable unless concern for blasts; then please obtain manual differential.
- 4 Female subjects of childbearing potential only.

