### 8.2 Criteria For Study Treatment Discontinuation

Subjects who discontinue participation in the clinical study on their own or subjects who are withdrawn by the investigator, for reasons other than completion of treatment, disease progression or toxicity, will be defined as premature withdrawals.

A subject will be discontinued from protocol therapy under the following circumstances:

- Any adverse event which, in the Investigator's opinion, requires termination of the study medication.
- Disease progression, unless at the discretion of the principal investigator (in collaboration with any co-sponsors or collaborators) continued treatment with study drug is appropriate.
- The subject becomes pregnant. Pregnancy will be reported along the same timelines as a serious adverse event.
- The subject uses illicit drugs or other substances, or takes part in activities that may, in the opinion of the Investigator, have a reasonable chance of contributing to toxicity or otherwise interfering with results.
- The development of a second malignancy that requires treatment, which would interfere with this study.
- The subject is lost to follow-up.
- Development of an intercurrent illness or situation which would, in the judgment of the investigator, affect assessments of clinical status and study endpoints to a significant degree.
- If subject desires to discontinue.

The Investigator will make every reasonable effort to keep each subject in the study unless it is in the subject's best interests to discontinue participation. If a subject is removed from the study or declines further participation, all EOT evaluations should be performed if the subject is willing and able to be assessed. A description of the reason(s) for withdrawal from the study must be recorded on the case report form (CRF). The Investigator should also ensure that all subjects are followed up for survival status after the Final Visit.

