#### 12.4 Analysis of Secondary Endpoints

Secondary endpoints include PFS, TTP, PRO and CBR. PFS is defined as the duration of time from start of treatment to time of progression or death, whichever occurs first. Development of new disease or progression in any established lesions is considered progressive disease, regardless of response in other lesions. All subjects surviving at the time of analyses without events will be censored at their last follow-up date. PFS along with the confidence intervals will be estimated using the Kaplan-Meier method. TTP will be reported as the length of time from the start of treatment until the evidence of disease progression. Clinical benefit will be described using subject reported outcomes using PRO Numerical Rating Scale 11 as well as reporting the clinical benefit rate (CBR), defined as the proportion of subjects experiencing of objective response (CR+PR) or stable disease  $\geq$  4months.

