fentanyl  gefitinib haloperidol ibrutinib  idelalisib imatinib indinavir  irinotecan isavuconazole  itraconazole ivacaftor ketoconazole lansoprazole lapatinib losartan lovastatin  lurasidone  macrolide antibiotics maraviroc  medroxyprogesterone methadone midazolam  midostaurin  modafinil nefazodone nilotinib olaparib ondansetron osimertinib paclitaxel palbociclib pazopanib quetiapine  quinidine  regorafenib romidepsin saquinavir  sildenafil  simvastatin  sirolimus  sonidegib				

UF-SC-001

2024-Aug-12

CYP3A4 substrates	Strong Inhibitors 	Moderate Inhibitors	Strong Inducers	Moderate Inducers
sunitinib tacrolimus  tamoxifen telaprevir temsirolimus teniposide tetracycline tipranavir  tolvaptan  triazolam  trimethoprim vardenafil  vemurafenib venetoclax  vinca alkaloids zolpidem				

 Certain fruits, fruit juices and herbal supplements (star fruit, Seville oranges, pomegranate, gingko, goldenseal) may inhibit CYP 3A4 isozyme, however, the degree of that inhibition is unknown.

[figure not shown]
Refer to [Section 4.3](#) regarding use of corticosteroids.

The effect of grapefruit juice (strong vs moderate CYP3A4 inhibition) varies widely among brands and is concentration-, dose-, and preparation-dependent.

Narrow therapeutic range substrates.

Sensitive substrates (drugs that demonstrate an increase in AUC of  $\geq 5$ -fold with strong inhibitors).

Appendix G: NUMBERED PAIN RATING SCALE 11

11-point Pain Numbered Rating Scale (NRS-11).

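### The patient-reported pain endpoint is a mean score not tied to baseline; taken by cycle or pooled, it could fall through selective dropout alone and should be a paired change from Cycle 1 Day 1

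*Combined protocol and SAP*

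**What the plan says.** Section 2.2.1 makes clinical benefit by patient-reported outcome a secondary objective. Its endpoint in Section 2.2.2 is "Numbered Pain Rating Scale 11 pain score mean". The analysis text in Section 12.4 reads "Clinical benefit will be described using subject reported outcomes using PRO Numerical Rating Scale 11", alongside the separate clinical benefit rate. Neither section names a change from baseline, an analysis visit, a set of subjects or a rule for missing scores. Intent-to-treat is stated in Section 12.3 for the response rate only.

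The Schedule of Events (Section 6.1) collects the scale at Cycle 1, at each later cycle and at EOT. It is not collected at screening, at the 28-day follow-up or in survival follow-up. Per-cycle scores stop with treatment, and Section 3.1 says "Treatment with Tazemetostat will continue until disease progression, unacceptable toxicity or withdrawal of consent or termination of study". Section 6.3 calls for EOT evaluations within 14 days of the last dose, including after discontinuation under Section 8.2. Section 8.2 qualifies this for subjects who are removed or decline to go on: "all EOT evaluations should be performed if the subject is willing and able to be assessed".

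**The concern.** The set of subjects giving per-cycle scores shrinks as treatment ends. A mean over whoever remains at a given cycle is therefore a mean over a different group from the one at Cycle 1. If subjects with more pain tend to leave sooner, the remaining group has lower scores and the mean drops although nobody has improved. Pooling all on-treatment visits has the same weakness, because subjects who stay longer contribute more scores.

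The trial has one open-label arm, so no control group would expose such a drop as an artefact. It could be described as clinical benefit, which is the objective the endpoint serves. The score needed to avoid this is already collected at Cycle 1, but the stated summary does not call for it.

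**Working it through.** **The plan's own figures.** None is given for the pain endpoint. The only design figures concern the response rate: continue with 3 or more responses in 9, and reject with 10 or more in 29. The rejection probability is the sum over x = 3 to 9 of P(X = x) × P(Y ≥ 10 − x), with X binomial on 9 and Y binomial on 20. It is 0.0485 at 21% and 0.804 at 45%, so the stated 5% and 80% reproduce. The pain endpoint does not enter that rule.

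**How fast the set shrinks.** Inputs: 29 subjects (Section 12.2), 28-day cycles, and exponential time on treatment (assumed). Two medians from the background serve as proxies: 17 weeks (PFS in MPNST on first-line chemotherapy, Section 1.2) and 5.5 months, about 23.9 weeks (PFS on tazemetostat in epithelioid sarcoma, Section 1.4.2). Expected number remaining = 29 × 0.5^(weeks / median).

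| | Week 16 (Cycle 5) | Week 24 (Cycle 7) |
|---|---|---|
| 17-week median | 15.1 | 10.9 |
| 5.5-month median | 18.2 | 14.5 |

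**What that can do to a raw mean.** Assume half the subjects have a fixed high score and half a fixed low score. The high-pain half leaves HR times faster, and the overall median is 17 weeks. Let x be the share of the low-pain half still on treatment at week 17. Then x + x^HR = 1, and at week t the remaining shares are x^(t/17) for the low-pain half and x^(HR·t/17) for the high-pain half.

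For HR 2, x = 0.618. At week 24 the shares are 0.507 and 0.257. With scores of 3 and 7 the mean is (3 × 0.507 + 7 × 0.257) / 0.764 = 4.35, against 5.00 at Cycle 1. The same formula gives these means at week 24:

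| Fixed scores | Cycle 1 | HR 1 | HR 1.5 | HR 2 | HR 3 |
|---|---|---|---|---|---|
| 7 and 3 | 5.00 | 5.00 | 4.61 | 4.35 | 4.01 |
| 6 and 4 | 5.00 | 5.00 | 4.80 | 4.67 | 4.51 |
| 5 and 4 | 4.50 | 4.50 | 4.40 | 4.34 | 4.25 |

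For scores of 7 and 3 the apparent fall is 0, 0.39, 0.65 and 0.99 points. For 6 and 4 at HR 3 it is 0.49. Pooling all on-treatment visits over Cycles 1 to 26 gives 4.66, 4.43 and 4.15 for scores of 7 and 3 at HR 1.5, 2 and 3. Within-subject change from Cycle 1 is 0.00 in every cell.

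**The same in whole subjects.** Fifteen subjects at 7 and fourteen at 3 give (105 + 42) / 29 = 5.07. If four and ten remain, the mean is (28 + 30) / 14 = 4.14. The raw mean has dropped 0.93, while the paired change in those 14 subjects is zero. If the 15 who left each gave an EOT score, the mean of all 29 last scores would again be 5.07.

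**The case against.** A reader might infer that the endpoint as written is biased toward showing pain relief. The documents do not support that. The plan never says that the mean is taken by cycle over those still on treatment. A Cycle 1 mean set against an EOT mean fits the wording equally well, and with complete EOT scores it shows no bias in the fixed-score illustration.

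Nor do the documents support the inference that subjects who progress leave no exit score. Section 6.3 calls for EOT evaluations on discontinuation, and Section 8.2 lists progression among the reasons. Section 8.2 also allows treatment past progression at the principal investigator's discretion. The willing-and-able condition means that some exit scores may be missing, not that they go uncollected.

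The bias is also conditional. At HR 1 the expected mean does not move, no passage links pain score to progression, and exits for toxicity or withdrawal need not follow pain. The spread of scores and the hazard ratios are assumptions. The 17-week proxy comes from chemotherapy-naive patients, and the tazemetostat sarcoma figure implies slower attrition.

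All of this stands. It limits the claim but does not remove it: the by-cycle and pooled readings are both open under the text, both are exposed, and neither section anchors the score to baseline.

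**Conclusion.** The point holds in a limited form. The endpoint is a mean with no stated use of the Cycle 1 baseline. Two natural ways of computing it would mix change in pain with change in who is being measured. The false fall arises only if higher-pain subjects leave treatment earlier, which is plausible because progression is a main reason for leaving but is not shown in the documents.

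The size is an illustration, not an estimate for this trial: about 0 to 1 point at week 24 for fixed scores of 7 and 3, hazard ratios of 1 to 3 and a 17-week median, and less if scores vary less. The endpoint is secondary and descriptive, with no test or threshold, so what is at risk is the account of clinical benefit. The primary response-rate decision is untouched. The change is worth making because a better summary is available from data already scheduled.

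**What to change.** In Sections 2.2.2 and 12.4, define the endpoint as within-subject change in the pain score from Cycle 1 Day 1. Summarise it descriptively as paired change at named cycles and at EOT, and give the last on-treatment change for every subject. Report the number contributing at each time point, and count subjects who have no later score rather than dropping them silently. A repeated-measures model is optional: with about 29 subjects, and around 11 expected at week 24 on the 17-week proxy, paired summaries are enough.

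The same edit can correct the pointer in Section 2.2.2, which cites Appendix I although the scale is Appendix G and the appendices end at H.

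The cost is a few lines of text and minor programming, with no new data or visits. The drawback is small numbers at late cycles, which the reported denominators would make visible.
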